In Balint groups, nurses explore strategies to better manage challenging patient-nurse relationships and enhance their interpersonal skills (Huang et al., 2020). These groups are particularly effective in raising awareness of the emotions and thoughts associated with patients perceived as "difficult" (Yousefzadeh et al., 2024). Balint-based interventions also provide social support by creating a relatively safe environment while respecting nurses' professional experiences (Lv, 2023). Moreover, considering nurses' working conditions, Balint-based interventions are regarded as easily implementable, time-efficient, and evidence-based approaches (Yang et al., 2021).

Rationale

Previous studies have primarily examined the effectiveness of Balint therapy among residents and medical students (Huang et al., 2020a; McCarron et al., 2024). In recent years, there has been growing interest in implementing Balint groups with nurses (Lu et al., 2020). Existing literature indicates that Balint therapy is effective in reducing burnout and enhancing self-efficacy (Shan et al., 2024), improving communication skills (Yang et al., 2021), and promoting quality of work-life among nurses (Huang et al., 2020). However, further research is needed to examine the long-term effects and sustainability of this intervention among nurses. To the best of our knowledge, this study represents the first application of a Balint-based intervention with nurses in the country, highlighting a gap in the literature regarding its effectiveness. Given the demanding working conditions of nurses, a Balint-based group intervention may provide meaningful support for their psychosocial well-being and facilitate positive patient care outcomes.

The current study aims to measure the effect of a Balint-based group intervention on burnout and communication skills in nurses. The research hypotheses are as follows:

H0-1: There is no significant difference in burnout levels between the intervention and control groups.

H0-2: There is no significant difference in communication skills between the intervention and control groups.

Study design

The study used a two-arm parallel-group randomized controlled design with pre-test and post-test measurements and follow-up assessments at one and three months.

Methods

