Participants were nurses recruited through purposive sampling in 2025. A power analysis was conducted to determine the required sample size for the intervention and control groups. Based on a previous study examining the effect of Balint group training on burnout (Huang et al., 2020), the minimum required sample size was calculated as 28 participants, with an alpha (α) level of 0.05, an effect size (d) of 1.70, and a power of 99%. Considering the nurses' shift schedules, potential attrition was anticipated.

All nurses working in hospitals across various cities nationwide where the study was conducted were invited to participate through announcements posted on social media platforms. The inclusion criteria were: (i) having worked as a nurse in the same clinical setting for at least one year and (ii) providing informed consent to participate. The exclusion criterion was the presence of a communication impairment that could hinder participation (e.g., hearing or speech disorder). The criteria for discontinuation from the study included: (1) voluntary withdrawal, (2) missing at least two sessions, and (3) incomplete or missing data on the study instruments.

A total of 50 nurses contacted the research team and underwent eligibility screening. Of these, 17 declined participation after learning that session attendance was mandatory, and three did

not meet the inclusion criteria. Ultimately, 30 nurses who met the inclusion criteria were enrolled in the study, taking anticipated attrition into account.

Randomization and prevention of bias

Participants were randomly assigned to either the intervention or control group at a 1:1 ratio using simple randomization. An independent academic not involved in the study generated a random number list via a computer program to minimize selection bias. Eligible nurses were then sequentially allocated to the intervention ($n = 15$) and control ($n = 15$) groups according to the random sequence. Group assignments were determined using a lottery method conducted by two independent academics unaffiliated with the study. The letter “X” represented the intervention group, while “Y” represented the control group. Due to the nature of the Balint group intervention, blinding of participants and researchers was not feasible. Nevertheless, allocation concealment was maintained: data were coded (Group X/Group Y) and analyzed by an independent statistician blinded to group assignments to minimize bias.

Procedure

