Data analysis was conducted using IBM SPSS Statistics for Windows, version 26.0 (IBM Corp., Armonk, NY, USA). The dataset was screened for missing values and assessed for normality assumptions prior to analysis. Differences between the intervention and control groups were examined using Pearson's chi-square test for categorical variables and the independent samples t-test for continuous variables. Fisher's exact test was applied when the expected cell count was less than five. A two-way mixed ANOVA was performed to evaluate between-group, within-time, and group \times time interaction effects. Bonferroni correction was applied for multiple comparisons. Effect sizes were reported using Cohen's d for within-group comparisons and partial eta squared (η^2) for the mixed ANOVA. The interpretation of partial eta squared values followed the classifications proposed by Cohen (1992): $\eta^2 \geq .01$ was considered small, $\eta^2 \geq .06$ moderate, and $\eta^2 \geq .14$ large. Statistical significance was set at $p < .05$.

Ethical considerations

Ethical approval for this study was obtained from the Bilecik Seyh Edebali University Non-Interventional Clinical Research Ethics Committee (19.09.2024 – 280361). Prior to participation, nurses were provided with detailed information about the purpose of the study, the procedures to be performed, and the voluntary nature of participation. Informed consent was obtained electronically from all participants via an online consent form. Participants were assured of confidentiality, the right to withdraw from the study at any time, and that their personal information would not be shared.

References

Cohen, J. (1992). Statistical power analysis. *Current Directions in Psychological Science*, 1(3), 98–101. <https://doi.org/10.1111/1467-8721.ep10768783>

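### The plan tests the arms against each other but specifies no between-group effect estimate or confidence interval at post-test, 1 month or 3 months

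*Combined protocol and SAP*

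**What the plan says.** The Rationale states two null hypotheses, both about the difference between arms. The first reads "H0-1: There is no significant difference in burnout levels between the intervention and control groups"; the second says the same of communication skills. The Rationale also says that "further research is needed to examine the long-term effects and sustainability of this intervention among nurses". The Study design section sets assessments at pre-test, post-test, one month and three months.

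The Statistical analysis section gives the main model: "A two-way mixed ANOVA was performed to evaluate between-group, within-time, and group" × time interaction effects. It adds that "Bonferroni correction was applied for multiple comparisons", without defining the family of comparisons. It names an independent-samples t-test for continuous variables, without saying which variables or which visits. For effect sizes it specifies Cohen's "d for within-group comparisons and partial eta squared", the latter for the mixed ANOVA. No confidence interval is mentioned anywhere in the document.

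The Methods section plans on "an effect size (d) of 1.70, and a power of 99"%, giving a minimum of 28 participants. Thirty were enrolled, 15 per arm. It notes that "potential attrition was anticipated" but gives no rate. Grounds for discontinuation include "missing at least two sessions, and (3) incomplete or missing data on the study instruments".

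**The concern.** The randomised comparison is tested, but its size and precision are not estimated. The effect sizes that the plan does name cannot take the place of that estimate.

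- **Within-group d** is the only signed effect size planned. It measures change within one arm, so it includes whatever would have happened without the intervention.
- **Partial eta squared** has no direction, and the interaction value covers all four assessments at once. It does not say at which visit the arms differ, or by how much.
- **The group term** averages over all four assessments, including the pre-test, where randomised arms are expected to be equal. This dilutes a real post-baseline difference.

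At stake is the question that the follow-up visits were added to answer: how large the difference is at one and three months, and how well it is known. With at most 15 nurses per arm the uncertainty is wide. A report limited to p-values and the specified effect sizes would not show it.

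**Working it through.** **Inputs from the documents:** d = 1.70, alpha 0.05, power 99%, N = 28, and 15 per arm enrolled (Methods); four assessments (Study design). **Assumptions, because the documents give no figure:** 12 complete per arm as an illustration of attrition; pre-post correlation ρ between 0.3 and 0.8; a true difference of 0.8 SD as an illustration; outcome SD set to 1.

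**1. The plan's own figure.** For a two-sided two-sample t-test at d = 1.70, power by noncentral t is 98.6% with 13 per arm and 99.1% with 14 per arm. So 14 × 2 = 28 reproduces the stated minimum. A one-sided two-sample test would need 12 per arm (24), and a paired test 9 nurses. The planning d is therefore inferred to be a between-group d, which the Methods section does not state. On that reading, the plan sizes the trial on a between-group d and reports a within-group one.

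**2. Within-group d with no treatment effect.** Suppose both arms change by 0.3 SD. With the SD of change as standardiser, d = 0.3 / √(2(1 − ρ)):
- ρ = 0.3: 0.3 / √1.4 = 0.25
- ρ = 0.5: 0.3 / √1.0 = 0.30
- ρ = 0.7: 0.3 / √0.6 = 0.39
- ρ = 0.8: 0.3 / √0.4 = 0.47

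The true between-group difference is zero in every case. The plan does not state the standardiser; with the baseline SD, d would be 0.30 throughout.

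**3. Group term.** With true differences of (0, 0.8, 0.8, 0.8) SD over the four assessments, the average is (3 × 0.8) / 4 = 0.6 SD. A sustained difference is reduced by a quarter.

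**4. Sign of partial eta squared.** The interaction sum of squares is (n/2) Σ(d_t − mean d)², where d_t is the difference at assessment t. Reversing every sign leaves it unchanged, so a sustained benefit and an equal sustained harm give the same value.

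**5. Expected unadjusted 95% CI half-width at one visit,** t(1 − 0.05/(2k), 2n − 2) × √(2/n), where k is the number of visits in the Bonferroni family:
- n = 15, k = 1: 2.048 × 0.3651 = 0.75 SD
- n = 15, k = 3: 2.546 × 0.3651 = 0.93 SD
- n = 12, k = 1: 2.074 × 0.4082 = 0.85 SD
- n = 12, k = 3: 2.591 × 0.4082 = 1.06 SD

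At 15 per arm, an observed between-group d equal to the planning value of 1.70 would have a 95% CI of 0.85 to 2.53 by noncentral t.

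**6. With baseline adjustment.** Multiply by √(1 − ρ²) and use 2n − 3 degrees of freedom. At n = 15 and k = 1:
- ρ = 0.5: 2.052 × 0.3651 × √0.75 = 0.65 SD
- ρ = 0.7: 2.052 × 0.3651 × √0.51 = 0.54 SD

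With k = 3 these become 0.81 and 0.67 SD. Allowing for chance baseline imbalance adds about 2%.

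**The case against.** The hypotheses are worded as tests, and the planned group and group × time terms address them. The t-test and Bonferroni sentences may well cover contrasts between arms at each visit. This stands: a reader might infer that the plan makes no between-group comparison, and the text does not support that. It does not close the gap, because on any reading those sentences name no estimate and no interval.

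Three other stronger readings should also be set aside.

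- *That a reader could never rebuild a baseline-adjusted difference from the report.* If arm means and SDs are published and within-group d uses the change SD, the pre-post correlation can be recovered: mean change divided by d gives the SD of change, and r = (SD₁² + SD₂² − SD_change²) / (2 SD₁SD₂). The plan does not state the standardiser, so neither possibility is settled. Randomisation also makes the unadjusted difference unbiased; adjustment mainly adds precision.
- *That the plan's labels would call one and the same effect anything from small to large.* For 0.8 SD at ρ = 0.3, partial eta squared is 0.058 against a cut-off of 0.06, but only if the observed means match the pattern exactly. With sampling noise, the expected values run from 0.087 at ρ = 0.3 to 0.197 at ρ = 0.8, which is moderate to large.
- *That partial eta squared cannot separate any time courses.* A sustained effect and a post-test-only effect of size D do give the same interaction sum, 0.75 D². That equality holds because in each pattern one assessment differs from the other three. A pattern (0, 0, D, D) gives 1.00 D². Signed within-group d, shown per visit for both arms, would also help to separate time courses.

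Finally, the Outcome measures section already reports reliability at the second follow-up, so any addition is probably a late reporting change. That limits what the fix can restore, but an interval is still informative.

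**Conclusion.** The point holds as a gap in estimation, not in testing. The only signed effect size specified is not the randomised contrast, and neither the size nor the precision of the difference at each visit is planned for. The uncertainty left unstated is large: an expected half-width of 0.75 SD at one visit with 15 complete per arm, 0.93 SD with Bonferroni over three visits, and 0.85 or 1.06 SD with 12 per arm. The 12 per arm and all correlations are assumptions. The absence of a between-group estimate and interval is read directly from the text and depends on none of them, nor on the inferred reading of the planning d. The change should be made; it does not call the planned tests into question.

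**What to change.** In the Statistical analysis section, add the baseline-adjusted between-group difference (ANCOVA per visit) in the Maslach Burnout Inventory total at post-test, 1 month and 3 months, each with a 95% CI. Add the same contrasts for the communication skills scale as secondary. Apply the plan's Bonferroni correction across the three visits. Keep within-group d as descriptive only. Label the addition post hoc if outcome data have been seen.

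The cost is one small extra model per visit for each outcome, on data probably already collected, beside the mixed ANOVA. Bonferroni widens each interval by about a quarter (0.93 / 0.75 = 1.24). Baseline adjustment recovers some or all of that, depending on the correlation: 0.81 or 0.67 SD at ρ = 0.5 or 0.7 with 15 per arm. A post hoc label is likely, so the change would improve estimation without restoring prespecification.
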